10 SURVEILLANCE MONITORING

During the course of the Stryker NTX Registry and thereafter until the centre has been closed, the monitor(s) possibly visit the Centre(s) recruiting patients into the Registry by prior arrangement. The following persons can be contacted at any time concerning any problems or queries.

- local clinical contact by email or fax or
- Clinical Study Manager_ [contact]

[contact]

The monitor shall be given unhindered access to monitor relevant source documents (including medical records) to enable complete data verification, but with respect to the patient's integrity as described in section 14.4.

11 ANALYSIS OF RESULTS AND REPORTS

Results obtained from the NTX Registry will be tabulated and statistically analysed by Stryker's Clinical Department using an appropriate statistical software package. An interim analysis of the data will be made once appropriate patients are included in the Outcomes Registry.

There will be 2 types of annual reports on register data. i) Stryker Clinical will prepare a report on the overall dataset ii) each Investigator will receive a confidential report from data from their own institute including benchmarks relative to the average without disclosure of the results of other departments.

Possible analyses of the data include:

- Safety during follow-up and Survivorship as described by Kaplan-Meier survival curves:
 - Adverse events: All intra-operative and post-operative adverse events will be recorded.
 - Survivorship with regard to the revision of the entire system or system components (e.g. insert only, tibia base plate only)
 - Survivorship with regard to re-operation without component exchange

Patient clinical outcome

 Standard clinical parameters and KSS (Knee Society Score) as well as patient questionnaires (EQ5D (EuroQol Group) and KOOS (Knee Injury and Osteoarthritis Outcome Score)) preoperatively and each follow-up visit.

11.1 Statistical Methodology

The patient's safety and survivorship of the implants during the follow-ups will be described by Kaplan-Meier survival curves:

- Survivorship with regard to the revision of the entire system or system components (e.g. insert only, tibia base plate only)
- Survivorship with regard to re-operation without component exchange
- o all other adverse events types can be separately considered as failures for Kaplan-Meier survival curve assessment.

In addition to the Kaplan Meier survival curves, the surgeons involved in the register will have the possibility to analyse the following statistical descriptions/comparisons:

- Demographic and pre-operative assessments
- Intra-operative assessments
- KSS (pain/motion score, function score).
- o Patient questionnaires: KOOS, EQ5D Quality of Life assessment
- Adverse events and device-related adverse events
- Revisions/removals

Frequency and percent distributions will be presented in tabular form for categorical variables. The mean, standard deviation, minimum and maximum values will be presented for quantitative variables.

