Surveillance design	International multicentre, prospective follow-up of a consecutive series of patients				
Objectives	Provide outcomes information with regard to surgical and implant performance and patient clinical outcomes of the patients who are eligible for a either a Total Knee Arthroplasty (TKA) replacement surgery involving either: • Scorpio NRG Total Knee System with X3 insert • Triathlon Total Knee System with X3 insert or Partial Knee Resurfacing (unicompartmental knee arthroplasty, UKA) involving: • Triathlon PKR (Partial Knee Resurfacing) System with X3 insert				

Study Duration	The length of surveillance and patient visit schedule is based on the routine procedures of the institution. The surveillance system is set- up to record data at 1, 3, 5, 7 and 10 years follow-up. The implant will be followed for 10 years or until it has to be revised, the patient dies or emigrates (unless the patient withdraws participation). Definition of revision: at least one part of the implant has to be revised.					
Participating institutions	Up to sixteen institutions willing to participate in the Stryker Clinical Registry need to recruit at least 20 patients and maximum 100 patients. Institutions must fulfil the local and international applicable regulatory requirements. Sufficient human and technical resources in the centre are expected to ensure optimal data collection.					
Number of Patients	Up to 1600 patients will be included (20-100 per centre). All patients eligible for either a Total Knee Arthroplasty (TKA) replacement surgery involving either: • Scorpio NRG Total Knee System with X3 insert • Triathlon Total Knee System with X3 insert or Partial Knee Resurfacing (unicompartmental knee arthroplasty, UKA) involving: • Triathlon PKR (Partial Knee Resurfacing) System with X3 insert who have been informed about this outcomes register and who freely consent to participate (with the signed and dated inform consent) will be enrolled in the register. Patients will be enrolled prospectively.					

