The main difference between the Triathlon Total Knee system and the Scorpio NRG Total Knee system is beside the use of a single A/P radius also the use of a single M/L radius design for the Scorpio NRG realizing a large contact area and higher rotational freedom in the two orthogonal planes.

The Single Radius and Soft Tissue guided motion philosophy, coupled with the latest generation highly cross-linked polyethylene (X3) as the material for the articulating surface has the potential to offer patients a longterm solution to their knee disability. X3 polyethylene preserves the mechanical strength, resists oxidation and shows extremely low wear rates.

Summary

The higher demands placed on current and new implants by the younger typically more active patient population emphasizes the importance for prostheses that show consistent long-term results. As the Stryker Knee systems are evolutionary in design and based on proven concepts and prior implant strategies, it is anticipated that they will demonstrate efficacy and safety in the long-term, however as for all new technology or design, a close overview of the long term performance and outcome is essential to prove this.

The aim of this Stryker Clinical Registry is to determine the Scorpio NRG, Triathlon and X3 component survivorship over years within a large European multicentre user group.

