Indication (for surgery)

Κ

The reason for surgery.

Kaplan-Meier A statistical method of carrying out a survivorship analysis that can take into

account 'censored' data, i.e. patient losses from the sample before the final

outcome is observed (for instance, if a patient dies).

KOOS Knee Injury and Osteoarthritis Outcome Score

KSS Knee Society Score

0

Outlier Data for a surgeon, unit or implant brand that falls outside of the defined

control limits.

Ρ

PA Peri-Apatite

Patella resurfacing Replacement of the surface of the patella (knee cap) with a prosthesis.

Patient consent A patient can only be included in the Stryker Clinical Registry where explicit

informed patient consent has been given.

Patient physical status See ASA.

PKR Partial Knee Resurfacing (Unicompartmental knee, UKA)

Primary knee replacement

First total joint replacement operation performed on any individual patient.

Prosthesis Orthopaedic implant used in joint replacement procedures, e.g. a total hip or a

unicondylar knee.

p-value A p-value is reported as a result of a statistical hypothesis test. It represents the

probability that any observed differences are due to chance. If the p-value is below a pre-determined cut-off (traditionally 0.05) the result is called

"statistically significant" and it can be concluded that the observed differences

are unlikely to be due to chance.

stryker

R

total joint prosthesis for whatever reason.

S

Standard Deviation (SD) The standard deviation is a measure of the spread of the data about the

average. The smaller the standard deviation, the less spread out the data.

Surgical approach Method used by a surgeon to gain access to, and expose, the joint.

Survivorship analysis A statistical method that is used to determine what fraction of a population,

such as those who have had a particular hip implant, has survived unrevised

past a certain time. See Kaplan-Meier.

Т

Thromboprophylaxis Drug or other post-operative regime prescribed to patients with the aim of

preventing blood clot formation in the post-operative period.

THA Total hip arthroplasty.

TKA Total knee arthroplasty (total knee replacement). Replacement of both tibial

and both femoral condyles, with or without resurfacing of the patella and with

or without cement.

Total condylar knee Type of knee prosthesis that replaces the complete contact area between the

femur and the tibia of a patient's knee.

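### Cheap improvement, low severity: section 11.1 should add cumulative incidence to Kaplan-Meier wherever the share of patients with an event is reported

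*Combined protocol and SAP*

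**What the plan says.** Section 11.1 (Statistical Methodology) says that patient "safety and survivorship of the implants during the follow-ups will be described by Kaplan-Meier survival curves". It lists three uses: revision of the whole system or of a single part, re-operation in which no part is exchanged, and, as an option, the remaining safety data, since "all other adverse events types can be separately considered as failures for Kaplan-Meier survival curve assessment". The synopsis also names Kaplan-Meier and no other time-to-event method. Neither place mentions cumulative incidence, competing events or a censoring rule. The other planned summary for such outcomes is descriptive: "Frequency and percent distributions will be presented in tabular form for categorical variables".

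Three other places bear on what the curves mean:

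- The summary in section 1 gives the aim as determining "component survivorship over years within a large European multicentre user group".
- The synopsis (Study Duration) follows the implant for 10 years or "until it has to be revised, the patient dies or emigrates". It counts a revision when "at least one part of the implant has to be revised".
- The glossary (section 15) describes censoring as loss of a patient before the final "outcome is observed (for instance, if a patient dies", so death is its example. Its entry on survivorship analysis speaks of the fraction of a population, "such as those who have had a particular hip implant, has survived unrevised" beyond a given time.

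**The concern.** Two quantities can be meant by the risk of an event by 10 years. One is the net risk: the probability of the event if nobody died, or had another part revised, first. The other is the cumulative incidence: the share of patients who actually have the event by then. Kaplan-Meier with deaths censored estimates the first, provided that censoring is independent. It does not estimate the second.

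For durability of the implant, the net risk is the natural quantity. Section 11.1 also applies the method to patient safety, re-operation and single-component revision, where a reader may well want to know how many patients were affected. The glossary's own description of survivorship, as a fraction of a population, can be read that way. At stake is an overstated share for these endpoints. Component-specific figures would also not add up to the figure for any revision.

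**Working it through.** **The plan's own figure.** The only relevant number is the enrolment cap: 16 centres x 100 patients = 1600, as stated. The documents give no revision, event, death or dropout rate. All rates below are therefore assumptions, shown over a range.

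**Set-up.** Hazards are constant over 10 years, and death and other censoring are independent of the event. With net 10-year risk r and 10-year mortality m:

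- h = -ln(1 - r)/10 and d = -ln(1 - m)/10
- one minus Kaplan-Meier, deaths censored = r
- cumulative incidence = h/(h + d) x (1 - exp(-10(h + d)))

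Example with r = 5% and m = 20%: h = 0.005129, d = 0.022314, h/(h + d) = 0.1869, and 1 - 0.95 x 0.80 = 0.24. The product is 4.49%.

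| 10-year mortality | Share if net risk is 5% | Gap (points) | Share if net risk is 30% | Gap (points) |
|---|---|---|---|---|
| 10% | 4.75% | 0.25 | 28.56% | 1.44 |
| 20% | 4.49% | 0.51 | 27.07% | 2.93 |
| 30% | 4.21% | 0.79 | 25.50% | 4.50 |
| 40% | 3.92% | 1.08 | 23.85% | 6.15 |

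Out of 1600 patients, the gap is about 4 to 17 at a 5% net risk and about 23 to 98 at 30%. A simulation of 400,000 patients at 5% net risk and 30% mortality gave 4.24%, against 4.21% by formula.

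**Comparison with sampling error.** The best-case 95% half-width, with no censoring, is 1.96 x sqrt(p(1 - p)/n). For p = 5% it is 1.07 points at n = 1600, 2.39 at n = 320 (16 centres x 20) and 4.27 for a centre with 100 patients. For p = 30% and n = 1600 it is 1.96 x sqrt(0.30 x 0.70/1600) = 2.25 points.

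**Timing.** If a 5% net risk falls only in years a to b, then h = -ln(0.95)/(b - a) and the share is exp(-d x a) x h/(h + d) x (1 - exp(-(h + d)(b - a))). Over 10% to 40% mortality, the ratio of one minus Kaplan-Meier to the share is 1.005 to 1.026 for events in year 1. It is 1.08 to 1.46 for events in years 5 to 10.

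**Component-specific revision.** Assume three exclusive first-revision categories with net risks of 3%, 3% and 4%.

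- Kaplan-Meier: the separate figures sum to 10.0%, while any revision is 1 - 0.97 x 0.97 x 0.96 = 9.67%.
- Cumulative incidence at 10% mortality, with the other categories and death competing: 2.75% + 2.75% + 3.69% = 9.19%, which equals the incidence of any revision.

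**The case against.** The strongest reply is that the plan contains no error here. Kaplan-Meier is valid for the stated aim, and no section names as an endpoint a cumulative share that allows for death. Section 11 presents its list as analyses that may be done, and the adverse event curves are optional. No threshold, decision rule or sample-size claim depends on the choice. With a 5% net risk and constant hazards, the gap is below the best-case half-width at 1600 patients except at 40% mortality. It is below it throughout at 320 or 100 patients. All of this stands, and it is why the point is only a low-severity improvement.

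The reply is weaker for commoner events. At an assumed 30% net risk the gap exceeds the 2.25-point half-width from 20% mortality upwards. Unlike sampling error, it does not shrink as patients are added.

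A reader might also infer several stronger points that the documents do not support:

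- **The registry will publish two figures for the patient share, both wrong.** Section 11 does not say that Kaplan-Meier results will be presented as a patient share. Section 12 does not fix the content of the final report. Section 11.1 states no denominator for its percentages.
- **The synopsis conflicts with the safety sections on follow-up after a revision.** Of sections 6.1.4, 7 and 7.1.1, only section 7 mentions 10 years. Section 6.1.4 lists form fields with no duration, and section 7.1.1 refers to the register's follow-up period. That does not establish a contradiction.
- **Loss linked to poor outcome strengthens the case.** Such loss can reverse the direction of the error, and cumulative incidence does not correct it. It therefore gives no support to this change.

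**Conclusion.** The point holds as a cheap improvement of low severity. Kaplan-Meier is the only time-to-event estimator planned, and no competing event is treated. It should stay for net implant survivorship and for comparing implants or centres. A reader might conclude that it is the wrong method for this registry, but the aim in section 1 does not support that.

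The limit concerns the share of patients with an event, where one minus Kaplan-Meier is too high if death or revision of another part can come first. The excess is 0.25 to 1.08 points at a 5% net risk and about 1.4 to 6.2 points at a 30% net risk, for 10% to 40% mortality over 10 years. These sizes rest on assumed rates, constant hazards and independent censoring. The excess is negligible for early events and larger for late ones.

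**What to change.** In section 11.1:

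1. Keep Kaplan-Meier, labelled as net implant survivorship, for revision and for comparing implants or centres.
2. Add Aalen-Johansen cumulative incidence with a 95% confidence interval wherever the proportion with an adverse event, a re-operation or a component-specific revision by a given time is reported.
3. Treat death as competing for every non-fatal endpoint.
4. For component-specific revision, classify by first revision, with revision of other parts competing. This builds on the revision definition already in the synopsis.
5. Treat emigration, withdrawal and loss to follow-up as censoring, and show the numbers lost beside the curves.
6. State whether the unit is the knee or the patient. The synopsis follows the implant but counts enrolment in patients, there are no exclusion criteria, and the glossary defines bilateral operations.

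The cost is SAP wording, a standard software routine and a second curve to explain. The change asks for no new data. Section 6.1.4 records onset date, revision and re-operation. Section 6.1.5 records date and reason of termination. Section 7.2 has death entered on both the adverse event and termination forms, and section 8 asks sites to find out whether patients lost to follow-up have died. The listed event dates are those of onset, occurrence and diagnosis. If a date of repeat surgery is wanted as the event time, Kaplan-Meier needs it equally.

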12 PUBLICATION OF RESULTS

By signing the Clinical Contract, the investigator agrees to the results of the outcomes registry being used for publication and for informing medical professionals. If necessary, names, addresses, qualifications and the role of the investigator in the outcomes registry shall be notified to the authorities.

The sponsor shall compile a final outcomes report.

The co-ordinating investigator and the principal investigators at each centre must confirm, by their signature, that they have read the report. They must confirm that to their knowledge, the report describes the outcomes results, and the way in which it has been conducted, accurately.

The method and timetable for compiling the publications shall be defined by mutual agreement between the Sponsor and the Investigators.

13 RISK BENEFIT ANALYSIS

13.1 Risk

There is no additional risk associated in participating in this outcomes register over and above that of the primary knee total arthroplasty or partial knee resurfacing (unicompartmental knee) procedure.

As in any surgical procedure, certain risks are associated with joint arthroplasty. These risks include but are not limited to: anaesthetic and post-anaesthetic reactions (such as hyperaemia), allergic reactions to prophylactic antibiotics or blood transfusions, damage to blood vessels or nerves, trochanteric or femoral fractures during implantation, perforation of the cortical wall, or death. Post-operatively, a patient may experience thrombophlebitis, pulmonary embolus, dislocation, pain, limp, component loosening, osteolysis due to wear debris or the need for additional surgery. Fracture of the prosthesis is a potential complication.

Adverse Events may necessitate re-operation, revision, arthrodesis of the involved joint, girdlestone or amputation of the limb.

13.2 Minimization of Risks

All components of the Scorpio NRG Total Knee System (with CR and PS insert), Triathlon Total Knee System (with CR and PS insert and CS insert) as well as the Triathlon Partial Knee Resurfacing System (Triathlon PKR) used in this post-market clinical registry have been CE marked (CE0086) according to the Medical Device Directive 93/42/EEC and therefore are approved for sale on the European market.

Pre-clinical, clinical, and mechanical testing of the above listed implants indicate that the above mentioned risks should not occur at a rate greater than that for any other type of knee arthroplasty reported in the literature.

Patients will be treated in the best medical judgement of the investigator, regardless of the outcomes registry.

13.3 Benefit

Patient benefits should include relief of pain and increase in functional capabilities, in addition to better assessment of the effect of prosthesis design and materials on functional and radiographic performance and bone remodelling around knee prostheses. This will increase the current scientific body of knowledge concerning total and unicompartmental knee arthroplasty.

14 ETHICAL CONSIDERATIONS

14.1 Declaration of Helsinki

The Surveillance will follow the guidelines as laid down by the "Declaration of Helsinki" (Declaration of Helsinki, October 2008) (**APPENDIX I** - DECLARATION OF HELSINKI).

In accordance with the Declaration of Helsinki, where applicable, all centres will gain written Ethics Committee approval prior to enrolling patients in the Surveillance either from the local responsible Ethics Committee at the investigator site or from an adequately constituted (according to ISO14155: 2011) independent Ethics Committee.

If a full Ethic Committee approval is not required, then a written confirmation of this is required from the responsible EC stating that data can be collected from that particular site.

14.2 Informed Consent

All recruited patients will sign and date the informed consent form before any investigational procedure or visit is performed. Only the latest ethics committee approved version is a valid document. The patient is provided with a copy of the information letter and consent form. The investigator is acquainted with the contents of the information sheet and answers patient questions regarding participation in the outcomes registry.

14.3 Patient Insurance (product liability)

Participating patients in this Surveillance are covered by Stryker SA product liability insurance.

14.4 Personal data protection

Stryker SA affirms and upholds the principle of the patient rights to protection against invasion of privacy. All data recorded in the CRFs or used for further evaluation are coded by patient number and age. Identification is restricted to authorized persons. In all data analyses the identity of patients will remain anonymous. Anonymous patient data may be stored and electronically processed by Stryker Clinical for the purpose of scientific evaluation and may be forwarded to a company and/or an authority located in- and outside Europe for registration and/or marketing purposes. Only authorized representatives of Stryker Clinical and health authorities will have allowed access to personal medical records for the sole purpose of checking the accuracy of data collected in the registry.

15 GLOSSARY

Α

ASA American Society of Anaesthesiology scoring system for grading the overall

physical condition of the patient, as follows: P1 – fit and healthy; P2 – mild disease, not incapacitating; P3 – incapacitating systemic disease; P4 – life

threatening disease; P5 – not expected to survive 24 hours.

В

Bilateral operation Operation performed on both sides, e.g. left and right knee procedures carried

out during a single operation.

BMI Body mass index. A statistical tool used to estimate a healthy body weight

based on an individual's height. The BMI is calculated by dividing a person's

weight (kg) by the square of their height (m²).

C

Case mix Term used to describe variation in surgical practice, relating to factors such as

indications for surgery, patient age and sex.

Cement The material used to fix cemented joint replacements to bone - polymethyl

methacrylate (PMMA).

Cemented Prostheses designed to be fixed into the bone using cement.

Cementless Prostheses designed to be fixed into the bone by bony ingrowth or ongrowth,

without using cement.

CI A confidence interval (CI) gives an estimated range of values which is likely to

include the unknown population parameter (e.g. a revision rate) being

estimated from the given sample. If independent samples are taken repeatedly from the same population, and a confidence interval calculated for each sample, then a certain percentage (confidence level: e.g. 95%) of the intervals

will include the unknown population parameter.

Ε

EQ-5D EQ-5D is a standardised measure of health status developed by the EuroQol

Group in order to provide a simple, generic measure of health for clinical and economic appraisal. The EQ-5D descriptive system comprises the following 5

dimensions: mobility, self-care, usual activities, pain/discomfort and

anxiety/depression.

F

Femoral component (knee) Portion of a knee prosthesis that is used to replace the articulating surface of

the femur (thigh bone).

Н

HA hydroxyapatite

Hazard ratio A comparative statistical measure of the instantaneous risk of experiencing the

event of interest (e.g. implant revision) between two groups (e.g. two different

products).

Hybrid procedure Joint replacement procedure in which cement is used to fix one prosthetic

component while the other is cementless.

ı

Image/computer guided

surgery

Surgery performed by the surgeon, using real time images to assist alignment

and positioning of prosthetic components

Indication (for surgery)

Κ

The reason for surgery.

Kaplan-Meier A statistical method of carrying out a survivorship analysis that can take into

account 'censored' data, i.e. patient losses from the sample before the final

outcome is observed (for instance, if a patient dies).

KOOS Knee Injury and Osteoarthritis Outcome Score

KSS Knee Society Score

0

Outlier Data for a surgeon, unit or implant brand that falls outside of the defined

control limits.

Ρ

PA Peri-Apatite

Patella resurfacing Replacement of the surface of the patella (knee cap) with a prosthesis.

Patient consent A patient can only be included in the Stryker Clinical Registry where explicit

informed patient consent has been given.

Patient physical status See ASA.

PKR Partial Knee Resurfacing (Unicompartmental knee, UKA)

Primary knee replacement

First total joint replacement operation performed on any individual patient.

Prosthesis Orthopaedic implant used in joint replacement procedures, e.g. a total hip or a

unicondylar knee.

p-value A p-value is reported as a result of a statistical hypothesis test. It represents the

probability that any observed differences are due to chance. If the p-value is below a pre-determined cut-off (traditionally 0.05) the result is called

"statistically significant" and it can be concluded that the observed differences

are unlikely to be due to chance.

stryker

R

total joint prosthesis for whatever reason.

S

Standard Deviation (SD) The standard deviation is a measure of the spread of the data about the

average. The smaller the standard deviation, the less spread out the data.

Surgical approach Method used by a surgeon to gain access to, and expose, the joint.

Survivorship analysis A statistical method that is used to determine what fraction of a population,

such as those who have had a particular hip implant, has survived unrevised

past a certain time. See Kaplan-Meier.

Т

Thromboprophylaxis Drug or other post-operative regime prescribed to patients with the aim of

preventing blood clot formation in the post-operative period.

THA Total hip arthroplasty.

TKA Total knee arthroplasty (total knee replacement). Replacement of both tibial

and both femoral condyles, with or without resurfacing of the patella and with

or without cement.

Total condylar knee Type of knee prosthesis that replaces the complete contact area between the

femur and the tibia of a patient's knee.

Trochanter Bony protuberance of the femur, found on its upper outer aspect.

Type (of prosthesis)

Type of prosthesis is the generic description of a prosthesis, e.g. modular

cemented stem (hip), patello-femoral joint (knee).

U

Uncemented See cementless.

Unicondylar arthroplasty Replacement of one tibial condyle and one femoral condyle in the knee, with or

without resurfacing of the patella.

Unicondylar knee replacement See Unicondylar arthroplasty.

Unilateral operation Operation performed on one side only, e.g. left knee.

